**Figure 1. Project Workflow**

After consent, enrollees will complete a ~10-minute computer-adaptive questionnaire, administered at the bedside on a tablet computer by the EDRA to determine adherence to current USPSTF recommendations for cervical cancer screening. The REDCap adaptive screening tool used will be identical to that which was used to gather our preliminary data. The enrollment process will categorize study participants into three groups: adherent, uncertain, or non-adherent (Figure 2). Women found to be adherent will be notified and their participation will conclude (i.e. no follow-up will be performed). Women found to be in the uncertain or non-adherent groups will then be randomized into one of two intervention conditions. Randomization will be automated in the REDCap survey instrument. All women found non-adherent will be referred to their usual care provider. If the patient does not have a usual provider of women's healthcare, she will be referred to UR WHP to receive appropriate screening. [name] (co-I) will maintain an expedited referral pathway to UR WHP for these subjects. [name] or one of the other health care providers at WHP will conduct the screening test. Women for whom adherence is uncertain (e.g. unsure, unable to remember) will be referred to their usual care provider or to UR WHP to confirm their adherence status. If, upon follow-up, the patient was confirmed adherent, she will be retroactively classified as adherent at baseline (though her uncertain status at screening will be retained in the dataset for potential secondary analyses). If confirmed non-adherent, the patient will be retroactively classified as non-adherent at baseline (with initial uncertainty retained). If the patient did not contact a provider to confirm adherence status (and did not remember her status in the 150 day interim), she will remain classified as uncertain.

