**b. Description of Interventions.** The proposed study pilots two interventions aimed at improving adherence to guidelines by encouraging screening outside of the ED. **Intervention A** only involves screening for adherence status and referral of uncertain and non-adherent patients for screening and/or confirmation of status and screening. **Intervention B** follows the Screening, Brief Intervention, and Referral to Treatment (SBIRT) model popularized in the substance use literature in the ED . The three components of the TPB intervention will be delivered via a series of text messages to mobile phones. Patients will receive a total of three text messages at 30-day intervals between the ED index visit and telephone follow-up survey at

150 days. Each text message will include a statement directed towards one of the TPB predictors of behavioral change intentions (Table 1) accompanied by a reminder to schedule cervical cancer screening with their primary provider or the WHP. Attitudes regarding cervical cancer screening will be addressed by emphasizing its efficacy for preventing morbidity.

Table 1 – Theory of Planned Behavior Texts to Participants in Intervention B

Element of the TPB	TPB portion of text	Scheduling portion of text
Attitudes about Screening	“Regular screening for cervical cancer is an extremely effective way to prevent cancer or identify early stages of cancer that can be effectively treated”	
Subjective Norms about Screening	“Over 80% of women across the country stay up-to-date with cervical cancer screening guidelines.”	Schedule cervical screening by calling your usual women’s health provider at {Participant-specific phone number} or with UR Women’s Health Practice at [contact]
Perceived Behavioral Control over Obtaining Screening	“Pap tests are available, without cost to you, at your women’s health provider or at the UR Women’s Health Practice.”	

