Subjective normative beliefs about screening will be addressed by emphasizing the preponderance of adherence to guidelines in the population. Perceived behavioral control over obtaining cervical screening will be addressed by discussing the accessibility and negligible financial burden of Pap tests. Women who have their own women’s health providers will be instructed to follow-up with these providers or utilize UR WHP, whichever they prefer. To facilitate patient follow through, the message will include hyperlinks to the telephone numbers of the patient’s women’s health care provider (if known) and the WHP.

**c. Follow Up.** All enrollees in the non-adherent and uncertain groups will receive a follow-up call at 150 days (Figure 3). The project coordinator will contact each of these participants by telephone for a brief REDCap questionnaire to determine if they underwent screening, if they learned that they did not require screening, and what barriers they perceived in getting screened or clarifying their adherence. Qualitative feedback regarding perceptions of the interventions will also be solicited from study participants in order to refine the interventions for future study. Relevant domains of feedback will include challenges to adhering with screening guidelines, comfort level with the intervention content discussed in the ED, which TPB message(s), if any, were perceived as most generative of intention to engage in cervical cancer screening, and participant recommendations for intervention revision. Telephone numbers will be confirmed in the ED during enrollment by the EDRA performing the enrollment (e.g., calling patient’s phone to be certain the number is correct), and up to 3 calls will be made to each of these patients to limit unnecessary attrition.

Study team members will use the EPIC medical record to confirm self-reported screening activities among the subjects successfully contacted at follow-up and who report a women’s health provider associated with UR Medicine. No confirmation will be sought among subjects reporting cervical screening with providers outside of the UR Medicine system.

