### **XI. DATA ANALYSIS**

**a. Plan of Analysis.** Based on previous research and our preliminary data, we anticipate  $\geq 18\%$  of patients will be non-adherent to screening guidelines. As such, we will enroll 450 patients to identify  $\geq 90$  non-adherent patients. To test **Specific Aim 1 - Hypotheses 1A/1B**, we will use (a) a one sample test of improvement in adherence at follow-up and (b) a two-sample comparison of post-intervention adherence across intervention conditions. These analyses will allow us to establish preliminary effect sizes for powering the subsequent NIH submission. The first test will compare % adherent at follow-up against a null value of 15% improvement (i.e., % of non-adherent subjects who would become adherent over 150 days without intervention). We think this is an unrealistically high null value, but it was chosen to avoid overestimating the impact of the study interventions. Using this null value, a one-tailed test with  $\alpha=0.05$ , and  $\geq 90$  non-adherent subjects across conditions, we will have power of 0.80 to observe improvement as small as 10% over the null (40% relative improvement). The second test will use  $\chi^2$  to compare conditions. Given a one-tailed test with  $\alpha=0.10$  and 45 non-adherent subjects in each condition, we will have power of 0.70 to observe a difference as small as 24% in adherence at follow-up. More importantly, we will establish a 95% confidence interval around the overall improvement rate (across conditions) with  $\leq 10.4\%$  margin of error and intervention specific rates of improvement with  $\leq 14.8\%$  margin of error. These intervals will allow us to calculate power for the subsequent trial under expected, ideal, and worst-case scenarios. Patients lost to follow-up will be considered intervention failures (i.e. non-adherent) in accordance with intention-to-treat principles. In order to test **Specific Aim 2 - Hypothesis 2**, we will use hierarchical, multinomial logistic regression to predict adherence at baseline. Given our sample size and an expected adherence rate of 0.80, at  $\alpha=0.05$ , we will have power  $\geq 0.70$  to observe odds ratios as small as 1.33. Any covariates demonstrating a  $p$ -value  $\leq 0.10$  will be addressed when refining the interventions for the subsequent NIH trial. **Specific Aim 3** is focused on the qualitative feedback data collected at the 150-day follow-up call. Qualitative data analysis of the feedback data will include open and axial coding under Grounded Theory principles examined in the context of subject demographic characteristics. The codes/concepts that emerge from these data will be examined in the context of the demographic characteristics of the subjects providing feedback. Results will then be used to refine the intervention protocols for the subsequent efficacy trial.

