
**b. Additional Analyses.** Supplemental analyses will be performed in order to strengthen interpretations of potential intervention effects. Specifically, we will perform the analyses described above among only those women who were referred to UR WHP (i.e., those without a usual provider of women's healthcare). Although we are not specifically powering our study around this subset of subjects, these analyses may help us identify success within this underserved population or important covariates/barriers than must be addressed when intervening with subjects lacking a usual women's healthcare provider. We will also corroborate subject self-reports of contact and screening using UR WHP records and subject eRecords (for those with providers associated with UR Medicine) as a way to further validate the findings observed. Finally, we will evaluate over-referral in our study by examining the percentage of women deemed to have uncertain adherence status who are reclassified as adherent, as well as those potential individuals deemed non-adherent in our study who find they are adherent through their women's healthcare providers. This rate of over-referral will be useful when evaluating the impact of the interventions on both subject health and clinical resource utilization.

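### Nothing in the plan keeps the follow-up caller from knowing the arm when self-reported screening is recorded, and the record check that could limit the resulting bias is only partial

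*Combined protocol and SAP*

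**What the plan says.** Section II.c (Follow Up) gives the 150-day contact to one role: "The project coordinator will contact each of these participants by telephone for a brief REDCap questionnaire to determine if they underwent screening". Feedback on the interventions is also sought, and one listed domain is "which TPB message(s), if any, were perceived as most generative of intention to engage in cervical cancer screening". Section XI.a confirms that this is the same contact, since Aim 3 "is focused on the qualitative feedback data collected at the 150-day follow-up call".

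The messages belong to one arm. Table 1 in section II.b is titled "Theory of Planned Behavior Texts to Participants in Intervention B", and Intervention A consists of screening and referral alone. Allocation comes from the platform that also carries the follow-up questionnaire: "Randomization will be automated in the REDCap survey instrument" (section II.a).

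On checking the answers, section II.c says: "Study team members will use the EPIC medical record to confirm self-reported screening activities among the subjects successfully contacted at follow-up", limited to those who report a women's health provider within UR Medicine. It then says: "No confirmation will be sought among subjects reporting cervical screening with providers outside of the UR Medicine system". Section II.c also plans a chart review of all enrollees covering the previous five years, again limited to UR Medicine providers and intended to validate self-report. Section XI.b places the use of records among the additional analyses: "We will also corroborate subject self-reports of contact and screening using UR WHP records and subject eRecords". No section says which source counts when the two disagree.

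**The concern.** The outcome for Hypothesis 1B is a spoken answer taken down by one person. If that person knows the arm at that moment, she may probe harder, accept a vague answer more readily or code an ambiguous one more generously for a woman who had the texts. Errors of that kind favour B, the direction the one-tailed test looks for.

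The stake is the B minus A comparison and the intervention-specific rates, which section XI.a intends to use in powering the next trial. A difference produced by recording would carry into that design.

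**Working it through.** **Is there a safeguard?** I looked for four things that would separate the outcome from the arm.

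| Safeguard | What the plan says |
|---|---|
| Caller masked to allocation | Not mentioned |
| Allocation hidden in the REDCap follow-up form | Not mentioned |
| Outcome items first and closed before feedback | Outcome items are described first in II.c, but no order is fixed and no lock is stated |
| Outcome classified from records, or a rule for disagreement | Partial EPIC check (II.c), supplemental (XI.b), no rule |

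**Inputs for the size.** From section XI.a: 45 non-adherent women per condition, a χ² comparison, one-tailed α = 0.10. Assumed, because the documents give no figure: a true screening rate p equal in both arms (15%, 25% or 40%); an excess d of false 'yes' answers in B; none in A; everyone reached; no correction from records unless stated.

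**The plan's own figure for this test.** Section XI.a states power of 0.70 for a 24-point difference. With pooled rate p̄ and n = 45,

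power = Φ{[d − 1.2816·√(2p̄(1−p̄)/n)] / √([pA(1−pA) + pB(1−pB)]/n)}.

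At 25% versus 49%: (0.24 − 0.1304)/0.0986 = 1.11, so power = 0.867. Across A rates from 10% to 50% the result is 0.85 to 0.94. The stated 0.70 does not follow from the stated inputs. That is a separate matter and does not affect this point.

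**Effect of biased recording.** The same formula gives the chance of declaring B better when d is recording error alone. At p = 25% and d = 5 points:

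- null standard error = √(2 × 0.275 × 0.725/45) = 0.0941
- threshold = 1.2816 × 0.0941 = 0.1206
- standard error with the bias = √((0.25 × 0.75 + 0.30 × 0.70)/45) = 0.0940
- chance = Φ((0.05 − 0.1206)/0.0940) = Φ(−0.75) ≈ 0.23

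Exact enumeration of all pairs of counts with the pooled z test gives:

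| True rate, both arms | No excess | +2.5 points | +5 points | +10 points |
|---|---|---|---|---|
| 15% | 0.103 | 0.173 | 0.263 | 0.475 |
| 25% | 0.102 | 0.158 | 0.230 | 0.413 |
| 40% | 0.103 | 0.149 | 0.207 | 0.355 |

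The +2.5 column is a 5-point excess of which records correct half (5 × 0.5). If records corrected every false 'yes', the rate would return to about 0.10. In women, 5 points is 0.05 × 45 = 2.25 and 10 points is 0.10 × 45 = 4.5.

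**The case against.** A reader might infer that the outcome is recorded with the arm already known. The documents do not say so. Section II.c describes the screening, status and barrier questions first and the feedback second. If the call runs in that order, the text-message item reveals the arm only after the outcome has been given. The questionnaire is not reproduced, so its branching and visible fields cannot be judged. This objection stands against the stronger reading. It does not supply a safeguard, because the order is not fixed and nothing hides allocation beforehand.

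The plan also has a real check. Women without a usual provider are referred to UR WHP, and the B texts offer that practice, so part of the reported screening can be verified. This reduces the risk for those women. It leaves out screening elsewhere, and women with their own provider are sent to that provider, who may be outside UR Medicine.

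The error rates in the illustration are assumptions. Women not reached count as non-adherent under section XI.a and cannot give a false 'yes', so incomplete follow-up would shrink the excess. Finally, this is a pilot whose plan gives more weight to confidence intervals than to the test. That lowers the stake of one p-value, but a biased B rate would shift its interval too.

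**Conclusion.** The point holds as a missing safeguard. One caller collects a self-reported outcome and feedback specific to Intervention B in one call, with no masking and no fixed order, and the record check is partial and is not stated to override self-report. Bias towards B from the caller's side is possible; its presence and size cannot be derived from the documents.

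The illustrative rates against a nominal 0.10 show only that two to five miscoded women in B would matter at this sample size. They rest on equal true rates of 15% to 40%, no false reports in A and complete follow-up, and, for all but the half-corrected case, no correction from records. The change is worth making because it costs little and the possible error runs in the hypothesised direction.

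**What to change.** In the REDCap follow-up form:

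1. Hide the allocation field from the caller.
2. Put the screening and adherence items first, with an identical script for both arms.
3. Lock those items before the intervention feedback section opens.

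State this in section II.c. It is a form change that needs no extra staff or calls, and the Aim 3 feedback is kept.

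Two limits remain. A woman may mention the texts unprompted. The change also does nothing about over-reporting by B women, who know that they were reminded. For that reason, add to section XI.b a B versus A comparison in which the outcome is classified from the UR Medicine record wherever one exists, and say how disagreements with self-report are handled. The record look-up is already planned, so the added cost is one analysis. It will cover only part of the sample and will miss screening done elsewhere, so it supplements the main test and does not replace it.

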### **III. CHARACTERISTICS OF THE RESEARCH POPULATION**

**a. Number of Subjects:** 450

**b. Gender and Age of Subjects:** Women age 21-65. Cervical cancer only occurs in women and cervical cancer screening is only recommended for women aged 21 – 65.

**c. Racial and Ethnic Origin:** We expect the racial and ethnic characteristics of our study population to mirror that of the general patient population of the Emergency Department at Strong Memorial Hospital.

**d. Vulnerable Subjects:** N/A

**e. Inclusion Criteria:**

- Women
- Age 21 - 65

**f. Exclusion Criteria:**

- Past hysterectomy with cervical removal
- Known infection with HIV (screening recommendations for women with HIV differ from the general population)
- Non-English speaking
- Inability to consent
- Lack of text-capable mobile phone and/or inability to use text function

### **IV. SUBJECT IDENTIFICATION, RECRUITMENT AND CONSENT**

**a. Method Of Subject Identification And Recruitment**

Emergency Department Research Associates (EDRAs) will use the EPIC eRecord system to screen adult patients that are registered in the ED at URMC for eligibility over a four-month period. Eligible women will then be approached by a representative of the EDRA program who will read a brief script describing the study and inviting the patient to enroll. Consent documentation will be completed for all enrollees. Based on previous studies with a similar level of patient involvement utilizing our EDRA program, we anticipate an enrollment rate of >85% of eligible participants, such that approximately 530 women will be approached.

**b. Process of Consent**

EDRAs will conduct the consent process using RSRB-approved consent documents. Subject will be encouraged to ask questions and to confirm comprehension. Consent documents will be stored in locked cabinets in the Emergency Medicine Research office suite in the Saunders Research Building.

### **V. METHODS AND STUDY PROCEDURES**

**a. Data Banking for Future Research Use**

Data obtained from the study will be stored for future analyses. This plan will be made expressly

clear in the consent document. All identifiers will be deleted from the data set after follow-up is completed.

**b. Costs to the Subject**

There will be no cost to study subjects.

**c. Payment for Participation**

There will be no payment to subjects for participation.

**d. Return of Individual Research Results**

Research results will not be provided back to the subjects.

## **VI. SUBJECT WITHDRAWALS**

Subjects will be advised in the written informed consent forms that they have the right to withdraw from the study at any time without prejudice. Subjects withdrawn from the study will not be replaced.

## **VII. SAFETY AND REPORTABLE EVENTS**

**a. Adverse Event Definition**

An adverse event is any symptom, sign, illness, or experience which develops or worsens during the course of the study, whether or not the event is considered related to study drug.

**b. Serious Adverse Event**

No serious adverse events related to this study can be reasonably expected to occur. A serious adverse event is defined as any adverse medical experience that results in any of the following outcomes:

- death;
- is life-threatening;
- requires inpatient hospitalization or prolongation of existing hospitalization;
- results in persistent or significant disability/incapacity;
- is a congenital anomaly/birth defect; or
- requires medical or surgical intervention to prevent permanent impairment or damage.

**c. Recording Adverse Events**

At each subject visit (i.e. index/enrollment visit in emergency department and follow-up phone call) the site study staff will assess adverse events by recording all voluntary complaints of the subject. At each study visit, the subject will be questioned directly regarding the occurrence of any adverse experience related to the study. All adverse events, whether observed by the Investigator, elicited from or volunteered by the subject, will be documented. Each adverse event will include a brief description of the experience, the date of onset, the date of resolution, the duration and type of experience, the severity, and the relationship to the study.

**d. Responsibilities for Reporting Serious Adverse Events**

No serious adverse events related to this study can be reasonably expected to occur. In the event of an SAE the RSRB will be notified immediately.

## **VIII. RISK/BENEFIT ASSESSMENT**

**a. Potential Risks**

The primary risk of this study is breach of confidentiality regarding the information you provide to us. The other potential risk is the bother of receiving text messages (study subjects will receive a maximum of 3 text messages) and of receiving the follow-up phone call.

**b. Protection Against Risks**

Only members of the study team will have access to the study information and all data will be kept in password-protected computers and/or in locked cabinets. No more than three attempts will be made to conduct the follow-up telephone call.

#### **c. Potential Benefits to Subjects**

The potential benefit a subject might have from participation is getting up-to-date on cervical cancer screening which is essential to identify treatable pre-cancerous lesions of the cervix before they progress to cancer.

#### **d. Alternatives to Participation**

There are no alternatives to choosing not to participate in this study. Standard of care in the ED will not be impacted by the decision to participate.

### **IX. CONFIDENTIALITY OF DATA AND INFORMATION STORAGE**

All electronic study data will be kept on password protected University drives. All paper data (e.g. consent documents) will be kept in locked storage cabinets in the Emergency Medicine Research suite in the Saunders Research Building.

### **X. RESEARCH INFORMATION IN MEDICAL RECORDS**

Research Data will not be included in the subject's medical record.

